Degenerative lumbar spinal stenosis (DLSS) is a condition involving narrowing of the space for the sagittal diameter of the spinal canal or nerve root canal for the spinal nerve or cauda equina secondary to degenerative changes [1-3]. DLSS is a common cause of gluteal and lower extremity pain and more likely to affect women and elderly people aged 60–70 years [4]. Because imaging evidence is not necessarily related to clinical symptoms, there are no specific epidemiological data for DLSS [5, 6]. According to the results of magnetic resonance imaging (MRI), 30–90% of asymptomatic adults may have spinal abnormalities including disc herniation, disc degeneration, or spinal stenosis [7]. DLSS is the most common type of spinal stenosis [1, 8]. The early symptoms of DLSS are soreness and pain in the low back, gluteal region, and posterior region of the thighs, which can be relieved after resting or changing posture. As patients with DLSS experience gradually aggravated symptoms, they may have neurogenic claudication with hypoesthesia and numbness in the lateral lower legs and feet; additionally, some patients may have bowel and bladder disturbances [9, 10]. DLSS patients have a poor quality of life, especially elderly patients [11]. In accordance with the guidelines of the North American Spine Society, treatment options comprise surgical therapy, epidural steroid injections and physical therapy, and transcutaneous electrical stimulation. According to some studies, the long-term efficacy of surgery is not superior to that of non-surgical therapy [12-15]. More studies are required to explore the efficacy of non-surgical therapy [16]. According to a systematic review [17] and recent studies [18, 19], acupuncture may improve the symptoms of patients and thus their quality of life; however, there is a lack of placebo-controlled and large-sample sized studies. More studies with a sufficient sample size are needed to provide evidence of the efficacy of acupuncture for treating DLSS.

3. Study Design and Objective

3.1 Objective

The aim of this study is to assess the effects and safety of acupuncture for relieving predominantly neurogenic claudication pain symptoms in patients with central DLSS.

3.2 Primary Hypothesis

We hypothesize the existence of difference between acupuncture and sham acupuncture (SA) in relieving neurogenic claudication pain symptoms among patients with central DLSS at week 6.

3.3 Study Design and Organizations

This is a multicenter, participants-blinded, parallel-group, randomized controlled study conducted in China.

The participants will be recruited in 5 clinical sites, which are Guang'anmen Hospital, China Academy of Chinese Medical Sciences; Shaanxi Provincial Hospital of Traditional Chinese Medicine; Guangdong Provincial Hospital of Traditional Chinese Medicine; The First Hospital of Hunan University of Chinese Medicine; and The Third Affiliated People's Hospital of Fujian University of Traditional Chinese Medicine. The study design and organization will be responsible by Guang'anmen Hospital, China Academy of Chinese Medical Sciences. A data coordination center will be established at Linkermed Pharm Technology Co., Ltd (Beijing, China) to monitor data management.

3.4 Study Time Frame

The duration of the study for each participant will be 31 weeks: 1 week before randomization as eligibility screening and baseline assessment, 6 weeks of treatment period, and 24 weeks of follow up period after the cessation of treatment (Figure 1. Study Design).

[figure not shown]

Figure 1. Study Design

There will be four timepoints of assessment:

Timepoint 1 will be scheduled during weeks -1 as eligibility screening and baseline assessment;

Timepoint 2 will be scheduled at week 6 at the end of treatment period;

Timepoints 3 and 4 will be scheduled at weeks 18 and 30, respectively, during 24-week follow-up period.

3.5 Trial Flow Chart

The trial flow chart is shown in Figure 2.

[figure not shown]

Figure 2. Trial Flow Chart

Abbreviations: DLSS, Degenerative lumbar spinal stenosis; RMDQ, Roland-Morris Disability Questionnaire; NRS, Numerical Rating Scale; SSSQ, Swiss Spinal Stenosis Questionnaire; HADS, Hospital Anxiety and Depression Scale.

4. Study Population

4.1 Diagnosis criteria

The diagnosis of central DLSS is made according to the North American Spine Society (NASS) [3], based on medical history, physical examination and related neuroimaging examination. An orthopedist from each center will be in charge of the diagnosis.

The detailed diagnostic evaluations are listed as following:

- (1) Participants should have a medical history of recurrent pain in buttock or lower extremity, with or without back pain.
- (2) Neurogenic intermittent claudication is a hallmark of DLSS. This is the tendency for symptoms, usually pain, to be exacerbated with walking, standing, and/or maintaining certain postures, and relieved with sitting or lying. The participants usually walk in a flexed or stooped position to relieve or reduce symptoms.
- (3) Neuroimaging examination like MRI or computed tomography (CT) shows structural narrowing of the intraspinal canal.

4.2 Inclusion criteria

Participants will be eligible if they:

- (1) Meet the requirements for a clinical diagnosis of DLSS combined with an MRI- or CT-based radiological diagnosis of central sagittal diameter stenosis of the lumbar spinal canal;
- (2) Have neurogenic intermittent claudication characterized by progressive pain of the buttocks and/or legs when standing or walking or with extension of the back, which are relieved upon sitting, lying down, or bending forward [20]; they always walk in flexion or hunchback posture;
- (3) Have pain of an intensity ≥ 4 in the buttocks and/or legs when walking, standing, or extending the back, as measured using the Numerical Rating Scale (NRS);
- (4) Have pain in the buttock and/or leg that is more severe than their pain in the lower back;
- (5) Have a Roland-Morris Disability Questionnaire (RMDQ) score of at least 7;
- (6) MRI (mainly) or CT scan showed the anterior posterior diameter of the canal was ≤ 12 mm;
- (7) Are aged 50-80 years;
- (8) Have provided signed consent and exhibit willingness to participate in the trial.

4.3 Exclusion criteria

Patients will be excluded if they have:

- (1) Congenital stenosis of the vertebral canal, indications of surgery for DLSS (e.g., segmental muscular atrophy, bowel and bladder disturbances), spinal instability requiring surgery, lumbar tuberculosis, lumbar metastatic carcinoma, vascular claudication, or vertebral body/vertebral stenosis segment compression fracture;
- (2) Severe vascular, pulmonary, or coronary artery disease with limited lower extremities motility;
- (3) Clinical comorbidities that could interfere with the collection of data related to pain and walking function such as fibromyalgia, chronic widespread pain, amputation, stroke, Parkinson's disease, spinal cord injury, and dementia;
- (4) Cognitive impairment, such that they are unable to understand the content of the assessment

scales or provide accurate data;

- (5) A history of lumbar surgery;
- (6) Plans to become pregnant within 12 months or are already pregnant;
- (7) Received acupuncture treatments for DLSS within the previous 30days;
- (8) Neurogenic intermittent claudication mainly manifesting as numbness, weakness, or paresthesia of the lower extremities instead of pain.

5. Subject Recruitment, Screening, Enrolment, and Group Assignment

5.1 Recruitment and Informed Consent

From March 2019 to June 2020, patients with DLSS will be recruited via newspapers, websites, WeChat and hospital posters in 5 centers over China. Patients who show interest in the study and meet the basic criteria of the study will sign the written informed consent form (see Appendix 1 Patient Inform Consent) before the formal screening process. The informed consent form will be reviewed and approved by institutional review boards at Guang'anmen Hospital, China Academy of Chinese Medical Sciences, and individual clinical site.

5.2 Screening and Baseline Assessment

On patients' official screening visit to hospital, they will sign the written informed consent form. Research assistants of each site will record their demographic information, course of disease and previous treatments. Orthopedists are responsible for the diagnosis and the differential diagnosis of DLSS.

Patients will receive a series of procedures to screen for eligibility, which will take approximately one week (week -1). To use the funds rationally and for consideration of the convenience of participants, the procedures will be scheduled step by step (Figure 3. Subject Flow Chart), and the eligibility criteria will be verified timely during the process. Those who fail in one step will not receive further screening.

To ensure the accuracy of eligibility screening and outcome assessment, it is imperative that patients avoid any therapy for DLSS throughout the trial. However, rescue medication can be used for emergency, except 48 hours before the assessment of pain and physical function.

The screening procedures include (in sequence):

- (1) The medical history, demographic information, and previous treatments;
- (2) Physical examinations;
- (3) RMDQ score and NRS score for the buttocks and/or legs, back;
- (4) MRI (mainly) or CT.

Participants who are still eligible after the examinations will complete the baseline outcome assessment questionnaires, which include the Swiss Spinal Stenosis Questionnaire (SSSQ), the Hospital Anxiety and Depression Scale (HADS), and participants' expectation assessment. The RMDQ and NRS will be completed again.

Note: Although the eligibility screening and baseline assessment are interpreted as Timepoint of assessment 1, participants might need to visit the hospital more than once during the process. The clinical site can arrange the procedures of examinations in accordance with the rapidity of each examination in their own hospital to save participants' time and visits to hospital.

[figure not shown]

Figure 3. Subject Flow Chart

Abbreviations: RMDQ, Roland-Morris Disability Questionnaire; NRS, Numerical Rating Scale; SSSQ, Swiss Spinal Stenosis Questionnaire; HADS, Hospital Anxiety and Depression Scale.

5.3 Group Assignment

Eligible participants will be randomly assigned either to the acupuncture group or the sham acupuncture (SA) group at week 0. The randomization will be completed by acupuncturists. The details of the central randomization will be described in 6.1 Randomization.

6. Randomization and Blinding

6.1 Randomization

Patients who provide informed consent and are eligible will be randomly assigned at a ratio of 1:1 to either the acupuncture group or the SA group using a central randomization system. The randomization scheme will be generated by Linkerm Pharm Technology Co., Ltd (Beijing, China) using statistical analysis software SAS 9.4 with “proc plan” program. The randomization sequence will be generated in varying block sizes and stratified by center. A comprehensive document describing the randomization scheme will be sealed in opaque envelopes by the staff who produce it and kept by another staff who takes no part in the clinical trial. The randomization scheme will not be checked by anyone except the senior system administrator. In each clinical center, a research assistant who takes no part in the treatment and outcome assessment will log in the web-based central randomization system to assess the random number and group allocation. All randomization will be masked until all data analyses have been conducted.

6.2 Blinding

The patients, outcome assessors, and statisticians will be blinded to the treatment allocation. Only acupuncturists are aware of the group allocation to administrate treatments.

Participants in the SA group will receive minimally invasive, superficial needle insertion of 2-3mm at the same acupoints used as the acupuncture group. Treatment protocol will be similar to that of the acupuncture group, and the acupuncturists will be trained to perform the same needling rituals in both groups. To test the success of blinding, within 5 minutes after treatment (Session 17 or 18) at week 6, participants will be told that there are two kinds of acupuncture methods, which are the traditional acupuncture where the insertion is relatively deep, and the minimal acupuncture where the insertion is relatively shallow; and participants will be randomly assigned to receive traditional acupuncture or minimal acupuncture at 50% chance respectively. Participants will then be asked to answer the question that “Do you think you have received traditional acupuncture in the past weeks?” The participants will be able to choose one of the following options as the answer: “Yes” or “No”.

7. Interventions

Sterile disposable steel needles (Hwato, Suzhou, China) will be used, and acupuncturists with at least 2 years of clinical experience will supply the treatment.

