Six questions in the symptom severity domain assess pain of the back, buttocks, legs, or feet as well as pain frequency, numbness, and weakness with scores ranging from 1 to 5, while one question assesses balance with possible scores of 1, 3, and 5. Higher scores indicate worse symptoms. The physical function domain assesses walking distance and ability to walk for pleasure, shopping, and getting around the house or apartment and from the bathroom to the bedroom. This domain has five questions with scores ranging from 1 to 4, and higher scores indicate less satisfaction. The satisfaction domain has four categories (very satisfied, somewhat satisfied, somewhat dissatisfied, and very dissatisfied) with a score range of 1–4 [31, 32].

(7) The proportion of participants who are somewhat satisfied and very satisfied based on the satisfaction domain of the SSSQ at weeks 6, 18, and 30;

According to satisfaction domain of the SSSQ, patients scoring 1.5–2.5 points are regarded as somewhat satisfied with the therapy, and those scoring 1.5 points or lower are regarded as very satisfied with the therapy [33].

(8) Changes in the HADS score from baseline to weeks 6, 18, and 30.

The HADS is validated and standardized for measuring the state of anxiety and depression [34, 35]. The HADS has two subscales with 14 items (7 items each), and a total score range of 0–21 with a range of 0–3 for each item. A score of ≥ 8 indicates the presence of anxiety and/or depression.

(9) Expectancy of acupuncture

Expectancy of acupuncture will be recorded at baseline. Participants will be required to answer two questions: “In general, do you believe acupuncture is effective for treating the illness?” and “Do you think acupuncture will help to improve your symptoms of DLSS?”

(10) Blinding assessment

Patients will be asked to answer the following questions after treatment (sessions 17 or 18) within 5 min: “Do you think you have received traditional acupuncture over the past 6 weeks?” The patients can answer “yes” or “no.”

(11) Safety assessment

Adverse events (AEs) related to acupuncture include severe pain, needle breakage, fainting, local hematoma, localized infection, and post-acupuncture discomfort with symptoms such as nausea, vomiting, palpitation, dizziness, headache, anorexia, and insomnia during the treatment period. AEs irrelevant to the treatment will also be recorded in detail throughout the trial.

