8.2.3 Six-week Treatment Phase

During the 6-week treatment (weeks 1-6), Timepoint of assessment 2 will be scheduled at week 6.

Participants will complete the RMDQ, NRS, SSSQ and HADS at week 6.

Within 5 minutes after treatment (sessions 17 or 18) at the week 6, the success of blinding will be assessed by outcome assessors at hospital.

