11.1 Sample Size Calculations

A sample size of 196 participants (98 in each group) was estimated to have provide at least 80% power at a 2-sided significance level of 5% to detect on a between-group difference of 2.5 points in the RMDQ score [23], assuming a standard deviation of 5.5 and a 20% dropout rate.

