3.2.2 Exclusion Criteria

- (1) Congenital stenosis of the vertebral canal, indications of surgery for DLSS (e.g., segmental muscular atrophy, bowel and bladder disturbances), spinal instability requiring surgery, lumbar tuberculosis, lumbar metastatic carcinoma, vascular claudication, or vertebral body/vertebral stenosis segment compression fracture;
- (2) Severe vascular, pulmonary, or coronary artery disease with limited lower extremities motility;
- (3) Clinical comorbidities that could interfere with the collection of data related to pain and walking function such as fibromyalgia, chronic widespread pain, amputation, stroke, Parkinson's disease, spinal cord injury, and dementia;
- (4) Cognitive impairment, such that they are unable to understand the content of the assessment scales or provide accurate data;
- (5) A history of lumbar surgery;
- (6) Plans to become pregnant within 12 months or are already pregnant;
- (7) Received acupuncture treatments for DLSS within the previous 30days;
- (8) Neurogenic intermittent claudication mainly manifesting as numbness, weakness, or paresthesia of the lower extremities instead of pain.

4. Schedule of Evaluation

	Study Period								
	Enrollment/Allocation week		Post-allocation week						
			Treatment week			Follow-up			
Timepoints	Week -1		Week 0		1	2	3	4	5
Enrollment									
Eligibility screen	x								
Informed consent	x								
MRI/CT	x								
Demographics	x								
Expectancy of acupuncture	x								
Allocation		x							
Interventions									
Acupuncture			x	x	x	x	x	x	
Sham acupuncture			x	x	x	x	x	x	
Assessments									
RMDQ	x						x	x	x
NRS	x						x	x	x
SSSQ	x						x	x	x
HADS	x						x	x	x
Blinding assessment			x	x	x	x	x	x	x
Safety assessment			x	x	x	x	x	x	x

Table 1. Enrolment, Intervention and Evaluation Schedules

Abbreviations: MRI magnetic resonance imaging, CT computed tomography, RMDQ Roland-Morris Disability Questionnaire, NRS Numerical Rating Scale, SSSQ Swiss Spinal Stenosis Questionnaire, HADS Hospital Anxiety and Depression Scale

5. Efficacy and Safety outcomes

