as well as pain frequency, numbness, and weakness with scores ranging from 1 to 5, while one question assesses balance with possible scores of 1, 3, and 5. Higher scores indicate worse symptoms. The physical function domain assesses walking distance and ability to walk for pleasure, shopping, and getting around the house or apartment and from the bathroom to the bedroom. This domain has five questions with scores ranging from 1 to 4, and higher scores indicate less satisfaction. The satisfaction domain has four categories (very satisfied, somewhat satisfied, somewhat dissatisfied, and very dissatisfied) with a score range of 1–4 [31, 32].

(7) The proportion of participants who are somewhat satisfied and very satisfied based on the satisfaction domain of the SSSQ at weeks 6, 18, and 30;

According to satisfaction domain of the SSSQ, patients scoring 1.5-2.5 points are regarded as somewhat satisfied with the therapy, and those scoring 1.5 points or lower are regarded as very satisfied with the therapy [33].

(8) Changes in the HADS score from baseline to weeks 6, 18, and 30.

The HADS is validated and standardized for measuring the state of anxiety and depression [34, 35]. The HADS has two subscales with 14 items (7 items each), and a total score range of 0–21 with a range of 0–3 for each item. A score of ≥ 8 indicates the presence of anxiety and/or depression.

(9) Expectancy of acupuncture

Expectancy of acupuncture will be recorded at baseline. Participants will be required to answer two questions: “In general, do you believe acupuncture is effective for treating the illness?” and “Do you think acupuncture will help to improve your symptoms of DLSS?”

(10) Blinding assessment

Patients will be asked to answer the following questions after treatment (sessions 17 or 18) within 5 min: “Do you think you have received traditional acupuncture over the past 6 weeks?” The patients can answer “yes” or “no.”

(11) Safety assessment

Adverse events (AEs) related to acupuncture include severe pain, needle breakage, fainting, local hematoma, localized infection, and post-acupuncture discomfort with symptoms such as nausea, vomiting, palpitation, dizziness, headache, anorexia, and insomnia during the treatment period. AEs irrelevant to the treatment will also be recorded in detail throughout the trial.

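### The only blinding question is tied to session 17 or 18, so early stoppers who still give week-6 outcomes go unasked and the blinding result may be biased, in an unknown direction

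*Combined protocol and SAP*

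**What the plan says.** Both documents place the question at the end of treatment. Protocol 6.2 puts it "within 5 minutes after treatment (Session 17 or 18) at week 6". Protocol 8.1.2, outcome (10), has it "after treatment (sessions 17 or 18) within 5 min", and SAP 5.1.2 repeats this: "Patients will be asked to answer the following questions after treatment (sessions 17 or 18) within 5 min". Protocol 8.2.3 adds the setting: "the success of blinding will be assessed by outcome assessors at hospital". The answer is Yes or No. Before it is put, participants are told that one method needles deeply and the other shallowly, with an even chance of each (protocol 6.2).

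Other provisions bear on who is reached:

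- Treatment is 18 sessions over six weeks (protocol 7.1), and a participant may leave at any point (protocol 9.2).
- Poorly compliant participants are still contacted by phone or message for outcomes (protocol 10.3, item 5).
- Efficacy is analysed in everyone randomised (SAP 6.2).
- Blinding data are described, not tested (SAP 6.3.4), and every variable gets a missing-value count (SAP 6.3.1).

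The schedules do not match. The "Blinding assessment" row has one mark in protocol Table 2 (8.2.1) and seven in SAP Table 1 (section 4).

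**The concern.** The primary outcome is a self-completed questionnaire, so the contrast with sham is only as good as participant blinding. Participants know from before the first session that two methods are in use (protocol 7.3, Step 1), and the methods differ a good deal in depth and manipulation (protocol 7.1 and 7.2). A sham participant who concludes that the needling is shallow has a reason to stop coming, and by stopping leaves the group that is asked.

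No text provides for asking at discontinuation. Blinding assessment is listed among the secondary outcomes, so the phone or message route might be thought to cover it, but a question put in hospital within five minutes of a late session does not fit that route. The plan could therefore report guesses from people still in treatment at the end, while the efficacy result also draws on people whose belief about their treatment was never recorded.

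**Working it through.** **Who is missed.** Taking the provisions together, there are three groups:

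1. Those who attend session 17 or 18, even after missing others: asked, and in the week-6 analysis.
2. Those who stop earlier but give week-6 outcomes under protocol 10.3, item 5: in the week-6 analysis, not asked.
3. Those who leave altogether: not asked. They also contribute no week-6 RMDQ, because the primary model uses observed changes (SAP 6.3.3).

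Group 2 is the real mismatch. The documents do not give its size.

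**Arm size.** The documents state no blinding figure; the planned arm size is used only to scale the illustration. Inputs from protocol 11.1: difference 2.5, SD 5.5, two-sided 5%, 80% power, 20% dropout.

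- Normal approximation: n = 2 × (1.96 + 0.842)² × (5.5/2.5)² = 2 × 7.85 × 4.84 ≈ 76 per arm; 76/0.8 = 95; total 190.
- Exact t-based calculation: 77 per arm; 77/0.8 = 96.25, so 97; total 194.

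The plan's 98 per arm (196) is two above the t-based total, in keeping with its claim of at least 80% power.

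**Shift in the blinding result, sham arm.** Let N = 98, m = number not asked, c = share correct (answering No) among those asked, and u = share of those not asked who would have been correct.

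Full-arm share = [(N − m)c + m·u]/N, so shift = full-arm share − c = (m/N)(u − c).

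A positive shift means that the reported figure overstates blinding. Assumptions: 5%, 10% or 20% not asked (m = 5, 10, 20 after rounding), and c = 30% or 50%.

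| Not asked | c | Shift if all would be correct (u = 1) | Shift if u = c | Shift if all would be wrong (u = 0) |
|---|---|---|---|---|
| 5 | 30% | +3.6 | 0 | −1.5 |
| 10 | 30% | +7.1 | 0 | −3.1 |
| 20 | 30% | +14.3 | 0 | −6.1 |
| 5 | 50% | +2.6 | 0 | −2.6 |
| 10 | 50% | +5.1 | 0 | −5.1 |
| 20 | 50% | +10.2 | 0 | −10.2 |

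Worked case, m = 20 and c = 30%: (78 × 0.30 + 20)/98 = 43.4/98 = 44.3% if all would be correct, and 23.4/98 = 23.9% if none would. With c = 50%: 59/98 = 60.2% and 39/98 = 39.8%. On the Bang index (2 × share correct − 1), the upper ends move from −0.40 to −0.11 and from 0.00 to +0.20. With u = 70% and m = 20, the shifts are +8.2 (c = 30%) and +4.1 (c = 50%).

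**The case against.** A reader might infer that reported blinding success will be biased upward. The documents do not support that. It requires early stoppers to guess correctly more often than those who stay, and there are no data on this. Sham participants who leave believing they had traditional acupuncture, or acupuncture participants who leave believing they had the minimal kind, would push the other way. Participants are also warned that they may feel nothing while the needles are in (protocol 7.3, Step 1), which may blunt suspicion, and treatment is free (protocol 10.3, item 3), which weakens one reason to stop. This part of the objection stands.

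Nor is it safe to say flatly that such people are never asked. SAP Table 1 shows several marks for blinding. Column positions in the copy available are unreliable, so this does not establish repeated asking, and the SAP's own text gives the single late timing. It does mean that the two schedules conflict.

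Size can be contested too. The sole attrition figure, "assuming a standard deviation of 5.5 and a 20% dropout rate", is a sample-size allowance, not split by time or arm, in a study running to week 30. As a share lost before session 17 it is nearer an upper value than an expected one. Some adverse inputs still do not show failed blinding: with 40% of those asked saying No, 20% unasked and 90% of those saying No, the arm reaches 0.40 × 0.80 + 0.90 × 0.20 = 50%, which is chance. At 40% with 78 to 88 respondents, the 95% half-width is itself about 10 to 11 points. These points limit the magnitude without closing the gap, since selective loss is a bias that a confidence interval does not cover.

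Finally, missing counts will be reported. That shows how many answers are absent, not what those people believed, and the SAP gives no denominator or rule for those not asked.

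**Conclusion.** The concern holds as one of selective missingness. On the text of both documents, the only blinding question depends on attending session 17 or 18, and people who stop sooner but supply week-6 outcomes are left out. The result would flatter blinding if suspicion of sham drives stopping; on the documents the direction is unknown.

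With 20 of 98 sham participants unasked, and 30% or 50% correct among those asked, the full-arm share of correct guesses could lie between 14.3 points above and 10.2 points below the reported share, with no difference if guessing and stopping are unrelated. These figures rest on assumed inputs and on the extreme cases for those not asked. The 20% is a planning value, not a strict bound, and the formula lets it be rescaled.

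No efficacy estimate or P-value changes, because blinding enters no test. What is affected is how far the sham comparison on a self-reported outcome can be trusted. This is a worthwhile, inexpensive improvement rather than a serious defect.

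**What to change.** - Put the blinding question to every randomised participant who can be reached, as the last item of the week-6 assessment, after the RMDQ and the other questionnaires, whether or not they attended session 17 or 18. Do this in person or through the phone or message contact already in protocol 10.3, item 5. Asking last also keeps the deep-versus-shallow explanation from coming before the primary outcome; protocol 8.2.3 does not fix that order.
- In the SAP, report guesses by arm for those treated through session 17 or 18, early stoppers, and those not asked, with all randomised as the denominator. Add a best/worst-case range for those not asked.
- Reconcile the blinding rows of protocol Table 2 and SAP Table 1 with each other and with the text.

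The cost is a wording change in both documents and one more item in a contact that is already planned. The drawback is that early stoppers will answer from recall, some by phone or message, so their answers are not fully comparable with those given minutes after a session. Reporting them separately makes that visible.
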